# 9.1.2 Updated Week 24 Interim Analysis and other interim analyses

For interim analyses such as for the SSD, DSMB and the Updated Week 24, the following modifications were made to more accurately calculate exposure and time at risk.

For an interim analysis with a database cutoff date,

- if the study participant is ongoing, the exposure calculation was database cutoff date date of first dose of study medication + 1 day. No data was presented in the analyses that was dated after the database cutoff date
- if the study participant was ongoing, the time at risk calculation was database cutoff date date of first dose of study medication + 1 day.

- if the study participant had discontinued from the study >28 days before the database cutoff date and had Q4W dosing at the time of study discontinuation, then the exposure was date of last dose of study medication date of first dose of study medication + 28 days
- if the study participant had discontinued from the study ≤28 days before the database cutoff date and had Q4W dosing at the time of study discontinuation, then the exposure was database cutoff date date of first dose of study medication + 1 day
- if the study participant had discontinued from the study >14 days before the database cutoff date and had Q2W dosing at the time of study discontinuation, then the exposure was date of last dose of study medication date of first dose of study medication + 14 days
- if the study participant had discontinued from the study ≤14 days before the database cutoff date and had Q2W dosing at the time of study discontinuation, then the exposure was database cutoff date date of first dose of study medication + 1 day
- if the study participant had discontinued from the study >70 days before the database cutoff date, then the time at risk was date of last dose of study medication date of first dose of study medication + 70 days
- if the study participant had discontinued from the study ≤70 days before the database cutoff date, then the time at risk was the database cutoff date date of first dose of study medication + 1 day.

- All TEAEs by primary SOC, HLT, and PT by ADAb participant status classification
- All serious TEAEs by primary SOC, HLT, and PT, overall and by Baseline weight group
- All TEAEs leading to study drug discontinuation by primary SOC, HLT, and PT, overall and by Baseline weight group
- All TEAEs leading to death by primary SOC, HLT, and PT, overall and by Baseline weight group
- Injection reaction TEAEs by primary SOC, HLT, and PT, overall and by Baseline weight group, further subdivided into injection site reactions and systemic reactions, with systemic reactions further subdivided into acute vs. delayed systemic reactions

The incidence of TEAEs will be presented as follows:

Injection reaction TEAEs by primary SOC, HLT, and PT, overall and by Baseline weight group, further subdivided into injection site reactions and systemic reactions, with systemic reactions further subdivided into acute vs. delayed systemic reactions

- All TEAEs by primary SOC, PT, and intensity, overall and by Baseline weight group
- All TEAEs by primary SOC, PT, and relationship, overall and by Baseline weight group
- All serious TEAEs by primary SOC, PT, and relationship, overall and by Baseline weight group
- All non-serious TEAEs by primary SOC, PT, and relationship, overall and by Baseline weight group
- All fatal TEAEs by primary SOC, PT, and relationship, overall and by Baseline weights
  group
- TEAEs occurring in at least 5% of study participants by primary SOC, HLT, and PT, overall and by Baseline weight group
- Non-serious TEAEs occurring in more than 5% of study participants by primary SOC and PT, overall and by Baseline weight group

Incidence tables summarizing TEAEs will include the number of TEAEs, number of study participants experiencing the TEAEs and percentage of study participants with the TEAE (all occurrences of the same event will be counted under the number of TEAEs but the study participant will only be counted once).

For disclosure on public registries (eg, ClinicalTrials.gov), information from the incidence tables of TEAEs and treatment-emergent SAEs will be published.

For the Updated Week 24 Interim Analysis only, in line with

#### 9.2.1 **TEAEs of interest**

The following are TEAEs of interest for this study and will be summarized in incidence and event rate tables (ie will include the number of events, the number and percentage of study participants with an event, the EAIR with associated 95% CIs and the EAER) as described below:

- 1) Serious infections, including opportunistic infections. Serious infections will be summarized using the previously described All SAEs table. No separate table is planned. In addition, opportunistic infections (including tuberculosis) will be presented in a table using UCB-defined search criteria.
- 2) Malignancies, including lymphoma. These will be presented in 2 tables using the criteria SMQ = "Malignant or unspecified tumours" and its subset, SMQ="Malignant tumours", respectively.
- 3) Congestive heart failure. These will be manually identified by the study physician from the previously described All TEAEs table. In addition, major adverse cardiac events (MACE) will be presented in a table. using UCB-defined search criteria and will include fatal and serious non-fatal myocardial infarction, cerebrovascular events and congestive heart failure.
- 4) Demyelinating-like disorders. These will be presented in a table based on the SMQ="Demyelination" in the TEAEs.
- 5) Aplastic anemia, pancytopenia, thrombocytopenia, neutropenia, and leucopenia. These will be presented in a table using the criteria SMQ = "Haematopoietic cytopenias" in the subset of SAEs.
- 6) Serious bleeding events. These will be presented in a table using the criteria SMQ = "Haemorrhage terms (excl laboratory terms)" in the subset of SAEs.
- 7) Lupus and lupus-like illness. These will be manually identified by the study physician from the previously described All TEAEs table and not tabulated separately.

**UCB** 

- 8) Serious skin reactions (eg. Stevens-Johnson Syndrome, toxic epidermal necrosis, anderythema multiforme). These will be manually identified by the study physician from the previously described All SAEs table and not tabulated separately.
- 9) Hepatic events. These will be summarized in a table that includes all TEAEs in the following SMQs: Cholestasis and jaundice of hepatic origin; hepatic failure, fibrosis and cirrhosis and other liver damage-related conditions; hepatitis, noninfectious; liver-related investigations, signs and symptoms; liver-related coagulation and bleeding disturbances.
- 10) Hypersensitivity reactions. These will be determined from all TEAEs that either emerged on the same day as or next day after the administration of study medication injection and summarized in a table. The PTs are: administration site hypersensitivity, documented hypersensitivity to administered product, drug hypersensitivity, hypersensitivity, hypersensitivity vasculitis, infusion site hypersensitivity, injection site hypersensitivity, medical device site hypersensitivity, type II hypersensitivity, type IV hypersensitivity reaction.
- 11) Anaphylactic reactions. These will be determined from all TEAEs that either emerged on the same day as or next day after the administration of study medication injection. Anaphylactic reactions will be summarized in a table using UCB-defined search criteria.

Further information regarding search criteria and algorithms is provided in the guidance document "AEs of Interest - Cimzia Program".

#### 9.2.2 AE of special interest

Potential Hy's Law is an AE of special interest for this study; the definition is below. The occurrence of this AE of special interest is dependent upon laboratory parameters, given that, the associated analysis of these AEs will be described in the Clinical laboratory evaluations section, PDILI paragraph in Section 9.3:

Potential Hy's Law, defined as  $\ge 3xULN$  alanine aminotransferase (ALT) or aspartate aminotransferase (AST) with coexisting  $\geq 2xULN$  total bilirubin in the absence of  $\geq 2xULN$ alkaline phosphatase (ALP), with no alternative explanation for the biochemical abnormality (ie, without waiting for any additional etiologic investigations to have been concluded). Follow-up information should be reported if an alternative etiology is identified during investigation and monitoring of the participant.

## Covid vaccine sensitivity analysis 9.2.3

A summary of the incidence and event rate (per 100 subject-years) of TEAEs by primary SOC, HLT, and PT, overall and by Baseline weight group will be presented which will exclude TEAEs occurring up to and including 7 days from the date of covid vaccination. The list of the PTs of these TEAEs to be excluded if reported with Mild or Moderate intensity are:

Table 9-2: Covid vaccination related adverse events for sensitivity analysis

ARTHRALGIA	INJECTION SITE INDURATION	
AXILLARY SWELLING	INJECTION SITE PAIN	

BACKACHE	MYALGIA
BODY TEMPERATURE INCREASED	NAUSEA
CHILLS	PRURITUS
DIARRHOEA	RASH
FEVER	TENDERNESS
HEAD DISCOMFORT	URTICARIA
HEADACHE	VOMITING
INJECTION SITE ERYTHEMA	
	andio

### 9.3 **Clinical laboratory evaluations**

All laboratory summaries described in this section will be provided for Reduced CZP Dose, Original CZP Dose, and Any CZP Dose and by Baseline weight group. All laboratory data will be listed.

Descriptive statistics for observed values and change from Baseline will be presented for each visit for the following hematology and biochemistry parameters:

- Hematology: RBC, hemoglobin, hematocrit, platelets, WBC, neutrophils, lymphocytes, monocytes, eosinophils, and basophils.
- Biochemistry: sodium, potassium, chloride, bicarbonate, total calcium, inorganic phosphorus, creatinine kinase, glucose, creatinine, uric acid, urea, total protein, albumin, ALP, gamma glutamyl transferase (GGT), AST, ALT, lactate dehydrogenase, bilirubin, and total cholesterol.

The following urinalysis parameters will be tested locally only: pH, protein, glucose, and blood. If abnormalities are found from the dipstick test, microscopic analysis (WBC, RBC, casts, crystals, and bacteria) will be performed, and these results will be listed. A summary of the shift from Baseline to end of treatment will also be provided for hematology and biochemistry parameters. Results will be classified as low, normal, or high based on the normal ranges provided by the central laboratory.

A summary of the incidence of markedly abnormal laboratory results by visit will be presented for hematology and biochemistry parameters. Details of markedly abnormal values will be listed by study participant and parameter for hematology and biochemistry variables for which there is at least 1 markedly abnormal result recorded. Definitions of markedly abnormal values are adopted from the UCB Therapeutic Area: Central Nervous System: Clinical and Laboratory Markedly Abnormal (MA) Values and are given below Table 9-3 for markedly abnormal hematology values and Table 9-4 for markedly abnormal biochemistry values).

Table 9–3: Definitions of Markedly Abnormal Hematology Values

Parameter (Unit)	Age Range Abnormal Definition			
		Low	High	
Hematocrit (%)	<2y	≤27	>45	
	2y-<18y	≤29	>47	
	≥18y	≤85% of LLN	≥115% of ULN	
Hemoglobin (g/L)	<2y	≤90	>150	
	2y-<18y	≤95	>160	
	≥18y	≤85% of LLN	≥115% of ULN	
WBC/Leukocytes	<12y	<3.5	>15.0	
(G/L)	≥12y	<3.0	>12.0	
Neutrophils Absolute (G/L)	>1m	<1.5	NA	
Lymphocytes (%)	<6m	≤30.0 →	NA	
	6m-<6y	≤22.0	NA	
	6y-<18y	≤12.0	≥80.0	
	≥18y	≤10.0	≥80.0	
Basophils (%)	>1m	NA	≥3.0	
Eosinophils (%)	>1m	NA	≥10.0	
Monocytes (%)	>1m	NA	≥20.0	
Platelets (G/L)	>1m	≤100	>600	
RBC/Erythrocytes	<2y	<3.0	NA	
(T/L)	≥2y	<3.5	NA	
y=year; m=month; LLN=lower limit of normal; ULN=upper limit of normal.				

Table 9–4: Definitions of Markedly Abnormal Biochemistry Values

Parameter (Unit)	Age Range	Abnormal Definition	
We.		Low	High
AST(SGOT) (U/L)	<14y	NA	>180
	≥14y	NA	>144
ALT(SGPT) (U/L)	1y-<18y	NA	>90

Table 9–4: Definitions of Markedly Abnormal Biochemistry Values

Parameter (Unit)	Age Range	Abnormal Definition	
		Low	High
	≥18y	NA	>123
Alkaline Phosphatase (U/L)	<4y	NA	>690
	4y-<10y	NA	>834
	10y-<17y	NA	>1174
	≥18y	NA	>432 (F) >933 (M)
GGT (U/L)	<6m	NA	>522
	6m-<1y	NA	>279
	1y-<13y	NA	>66
	13y-<18y	NA ZilO	>126
	≥18y	NA 4 objice	>255
Total Bilirubin (umol/L)	>1m	NA OF THE STATE OF	≥25.656
Total Protein (g/L)	2m-<1y	<30	>100
	≥1y	₹ 43	>100
Albumin (g/L)	<1y	<16	>60
	≥1y	<24	>70
Urea (mmol/L)	<1y	NA	>7.014
	≥1y x 2 (1)	NA	>10.02
Creatinine (umol/L)	1y-<10y	NA	>79.56
	10y-<16y	NA	>123.76
30	≥16y	NA	>141.44
Calcium (mmol/L)	<1y	<1.725	>3.05
of De	1y-<18y	<1.85	>2.925
Calcium (mmol/L)	≥18y	≤1.975	≥2.775
Lactate dehydrogenase (LDH) (IU/L)	2-17y		>1300
Phosphorus (mmol/L)	<1y	<0.5814	>2.6486
	≥1y	<0.5814	>2.3902
Potassium (mmol/L)	<1y	<3.0	>6.5

Confidential

Table 9-4: Definitions of Markedly Abnormal Biochemistry Values

Parameter (Unit)	Age Range	Abnormal Definition	
		Low	High
	≥1y	<3.0	>5.8
Sodium (mmol/L)	>1m	≤130	≥150
Glucose (mmol/L)	>1m	<2.775	>9.99
Total Cholesterol (mmol/L)	1y-<18y	NA	>6.475
	≥18y	NA	>7.77
Uric Acid (umol/L)	<1y	NA	>457.996
	1y-<13y	NA	>386.62
	13y-<18y	NA	>511.528
	≥18y	NA	>404.464 (F)
		a disconnection of the second	>571.008 (M)
Creatine Kinase (CPK) (IU/L)	2-17y	OPT application	>600
y=year; m=month; F=fe	emale; M=male.	O tiol	

Reference: Based on CTCAE version 5.0

PDILI IMP discontinuation criteria as outlined in the Appendix of Protocol Amendment 9 will be evaluated at all laboratory assessments, for all study participants. The number and percentage of study participants meeting PDILI criteria will be presented. The following criteria will be presented:

- AST or ALT  $\geq$  3xULN and Total Bilirubin  $\leq$  2xULN
- AST or ALT  $\geq$  3xULN and Total Bilirubin  $\geq$  2xULN
- AST or ALT  $\geq$  3xULN and Total Bilirubin  $\geq$  2xULN and Alkaline Phosphatase < 2xULN (Hy's Law if all criteria met at the same visit)
- AST or ALT ≥5xULN

Any data that meets the PDILI criteria or is captured regarding PDILI will be listed. Any data that is captured as being a suspected hepatic event will be listed.

A listing of when blood and urine samples were taken as well as serum pregnancy tests were performed will also be produced.

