## 2.3

This is a Phase 3, multicenter, open-label study to assess the PK, safety, and efficacy of CZP in children and adolescents with moderately to severely active pcJIA.

The study population will consist of study participants 2 to 17 years of age upon enrollment with a minimum weight of 10kg (22lb) (except in Russia, where the study population will consist of study participants 6 to 17 years of age upon enrollment with a minimum weight of 15kg [33lb]). Study participants must have had onset of signs and symptoms consistent with pcJIA and initiation of pcJIA treatment for at least 6 months prior to Baseline. Active pcJIA disease is defined as  $\geq 5$  joints with active arthritis including: polyarthritis rheumatoid factorpositive, polyarthritis rheumatoid factor-negative, extended oligoarthritis, juvenile psoriatic arthritis, and enthesitis-related arthritis (ERA). Study participants cannot have had active uveitis within the last 6 months prior to Baseline. In addition, study participants must have had an inadequate response to, or intolerance to, at least 1 disease-modifying antirheumatic drug (DMARD).

The study consists of a Screening Period of up to 4 weeks; eligible study participants will then enter an open-label Treatment Period which will continue until the approval of the marketing application for the indication of pcJIA in the study participant's country or region or closing the study by UCB. A Final Visit will be conducted 12 weeks after last dose of

implementing Protocol Amendment 8. For the study participants who switch to the 16-week schedule, the date of the first visit of this schedule will be captured on the "Stude" Participation" CRF module. Of note the participant of the particip The table below shows the data collection schedule prior to Protocol Amendment 8 and after (the new 30 study participants on Original CZP Dose) will remain on the original visit schedule throughout the study.

Table 2-2: Visit Schedule

Collected/ Assessed/ Administered at	Prior to Protocol Amendment 8 a	Following Protocol Amendment 8
Most parameters	Screening, Baseline, Weeks 4, 8, 12, 16, 20, 24, 32 and every 8 weeks thereafter, the Early Discontinuation/End of Treatment Visit, and the Final Visit	Screening, Baseline, Weeks 4, 8, 12, 16, 20, 24, 32 and every 16 weeks thereafter, the Early Discontinuation/End of Treatment Visit, and the Final Visit

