Continuous variables will be summarized with the mean, standard deviation, median, minimum, and maximum. For CZP plasma concentrations and CRP, the geometric mean and geometric coefficient of variation (CV) will be presented.

Due to shifts in visit schedules per protocol amendments that were adopted at different times for different sites and study participants, some visits/ time points had very few study participants assessed. For categorical and continuous efficacy variables presented by visit/time point, if the visit/time point for the Any CZP Dose group contains 19 or fewer study participants with non-missing data, those visits/ time points will not be displayed in the efficacy tables or plotted in figures for Reduced CZP Dose, Original CZP Dose and Any CZP Dose groups. All information will appear in the listings.

Mean, standard deviation, and median will be displayed to 1 more decimal place than collected in the case report form (CRF). Minimum and maximum values will be displayed to the same level of precision as collected in the CRF. Percentages will be calculated using the number of study participants in the relevant population or subgroup as the denominator. Presentation of percentages will be to 1 decimal place. Percentages will not be presented if the frequency count is 0.

No formal statistical hypothesis testing will be performed. Ninety-five percent confidence intervals (CIs) for the percentage of responders will be calculated using the exact binomial method.

For certain laboratory parameter results that are collected as either "<XX.X" or ">XX.X", if descriptive statistics are calculated for the parameter, the XX.X will be used in the calculation

The classification of AEs occurring on the same date as a dose change will belong to the period of the dose change.

In addition, for other subgroup analyses (e.g. Baseline age group, concomitant MTX use, etc.), data will be generally presented by the specified subgroups pooling across all weight groups (with the exception of PK analyses which are specified in the corresponding sections).

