  - Period G for study participants with dose reduction and without dose escalation; and
  - Period H for study participants with dose reduction and dose escalation.

- Complete Reduced CZP Dose: includes time at risk during all periods of exposure to Reduced CZP Dose for all study participants (periods A, B, C and D); use the following formulas:
  - Period A for study participants enrolled on Reduced CZP Dose without dose escalation;
  - Period B for study participants enrolled on Reduced CZP Dose with dose escalation;
  - Period C for study participants enrolled on Original CZP Dose with dose reduction and without dose escalation; and
  - Period D for study participants enrolled on Original CZP Dose with dose reduction and dose escalation.
- Complete Original CZP Dose: includes all time at risk during all periods of exposure to Original CZP dose for all study participants (periods E, F, G H and J); use the following formulas:
  - Period E for study participants enrolled on Reduced CZP Dose with dose escalation;
  - Period F for study participants enrolled on Original CZP Dose without dose reduction;
  - Period G for study participants enrolled on Original CZP Dose with dose reduction and without dose escalation; and
  - Period H+J for study participants enrolled on Original CZP Dose with dose reduction and dose escalation.

The extent of study drug exposure will be summarized for the Reduced CZP Dose, Original CZP Dose, and Any CZP Dose groups. Exposure over time will be presented as follows: >0 months,  $\geq 6$  months,  $\geq 12$  months,  $\geq 24$  months,  $\geq 36$  months,  $\geq 48$  months, and  $\geq 96$  months. In line with

response, the extent of study drug exposure as well as exposure over time were presented by Complete Original CZP Dose and Complete Reduced CZP Dose.

Study medication administration will be listed.

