# 9.4 Vital signs, physical findings, and other observations related to safety

## 9.4.1 Vital Signs

Vital signs will be measured within approximately 15 minutes prior to dosing, and in addition (following implementation of Protocol Amendment 3), pulse and blood pressure only will be

measured approximately 30 minutes after dosing with study medication. Study participants should be sitting for at least 5 minutes prior to and during the collection of blood pressure and pulse rate measurements. Vital signs to be collected are pulse, systolic/diastolic blood pressure measurement, and temperature.

For pre-dose measurements, if more than one results appears for a specific visit, then the pre-dose results are averaged. The same will occur for post dose measurements. All data will be listed, including the averages. If measurements are labeled as pre-dose in the CRF, but when compared to dosing, it is actually post-dose, the analysis label will reflect a post dose measurement. The same will occur for post-dose measurements.

Descriptive statistics for observed values and change from pre-dose to post-dose pulse and blood pressure when available, will be presented for each visit for each vital sign parameter.

Vital signs summaries will be provided for the Reduced CZP Dose, Original CZP Dose, and Any CZP Dose) and by Baseline weight group.

A summary of the incidence of markedly abnormal vital signs results by post-baseline scheduled visit will be presented for temperature, blood pressure, and pulse rate parameters. Details of markedly abnormal values will be listed by study participant and parameter for which there is at least 1 markedly abnormal result recorded. Definitions of markedly abnormal values are given below in Table 9–5.

Markedly abnormal high temperature is >40.0 degrees Celsius (>104.0 degrees Fahrenheit) while a markedly abnormal low temperature is 32-35 degrees Celsius (89.6-95 degrees Fahrenheit). Vital signs data will be listed, including the flagging of markedly abnormal values.

Table 9–5: Definitions of Markedly Abnormal Vital Signs Values

Parameter	Age Range	Abnormality Criteria
Pulse Rate	3y<	<60
(beats/minute)	<12y	>130
Ċ.	12y -	< 50
7/0	<17y	≥ 120
Jedie	≥17y	<60
		>100
Systolic Blood	3y -	<80
Pressure	<12y	>140
(mmHg)	12y -	<90
	<17y	>160
	≥17y	<90
		>140
		>160
	Зу -	<50
	<12y	>80

Parameter	Age Range	Abnormality Criteria
Diastolic Blood	12y - <17y	< 50 ≥105
Pressure	≥17y	<50
(mmHg)		>90
		>100

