10.3.13.2 Final Analysis

In the JIA Pain VAS, study participants 12 to 17 years old at Baseline are asked the following question, "How much pain have you had because of your illness today (acute version)/in the past week (standard version)?" (as applicable). The study participant should then place a mark on a 100mm VAS to indicate the severity of the pain, where 0 = "no pain" and 100 = "very severe pain".

Descriptive statistics of the observed values and change from Baseline will be presented separately for the acute and standard versions (See Protocol Amendment 9, Section 11.13) for each of the specified visits.

Study participants who are past 17 years old while still on the study will continue to be administered the JIA Pain VAS.

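### The age bands for markedly abnormal values leave ALP, LDH, CK, pulse and blood pressure without a limit at some ages on study, and give two unlabelled upper blood-pressure limits from age 17

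*SAP*

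**What the plan says.** Section 9.3 promises a by-visit incidence summary of markedly abnormal hematology and biochemistry results, defined by age band in Tables 9-3 and 9-4. Section 9.4.1 promises the same for vital signs, defined in Table 9-5.

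- **ALP (Table 9-4):** bands for <4y and 4y-<10y, then "10y-<17y NA >1174", then ≥18y with separate female and male limits.
- **LDH and CK (Table 9-4):** one row each, for example "Creatine Kinase (CPK) (IU/L) 2-17y". There is no adult row.
- **Pulse, systolic and diastolic pressure (Table 9-5):** bands 3y-<12y, 12y-<17y and ≥17y. The first systolic entry reads "Systolic Blood 3y - <80". In the ≥17y band systolic has both >140 and >160 as upper limits, and diastolic both >90 and >100.

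Section 2.3 enrols "study participants 2 to 17 years of age upon enrollment with a minimum weight of 10kg" (6 to 17 years in Russia). Section 9.1.1 states "Exposure over time will be presented as follows: >0 months" and continues to ≥96 months. Section 10.3.13.2 foresees adults on study: "Study participants who are past 17 years old while still on the study will continue to be" given the adolescent pain scale.

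Section 3.1 takes percentages over the relevant population or subgroup. Neither Section 9.3 nor Section 9.4.1 says which age, at the visit or at Baseline, selects the row.

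**The concern.** A band table used to flag values must give exactly one rule at every age at which a participant can be observed. These tables fail in two ways. At some ages there is no rule, so a value of any size goes unflagged and the participant counts as not abnormal. From 17 years there are two upper blood-pressure limits and no rule for choosing between them, so two programmers could follow the SAP faithfully and produce different tables.

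Safety is a primary objective, and vital-sign abnormalities are a named safety variable in Section 2.2.3.2. The final analysis covers long follow-up of children and adolescents who age through these bands.

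**Working it through.** There is no sample size, power or test to reproduce; Section 3.1 says "No formal statistical hypothesis testing will be performed". The check is of coverage and uniqueness.

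**1. Coverage.** Each age-banded row of Tables 9-3, 9-4 and 9-5 was coded as an age interval, with 2-17y read as 2 to <18. Each was searched monthly from age 2 to 30 for ages with no limit. Only these gaps appear; every other parameter that has a row is covered from age 2.

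| Parameter | Uncovered ages | If age at visit selects the row | If age at Baseline selects the row |
|---|---|---|---|
| ALP | 17 to <18 | all observed while 17, at those visits | those enrolled at 17, throughout |
| LDH, CK | 18 and over | all observed from the 18th birthday | no one |
| Pulse, systolic, diastolic | 2 to <3 | those enrolled at 2, until they turn 3 | those enrolled at 2, throughout |

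**2. Uniqueness.** In whole mmHg, systolic 141-160 at ≥17y is flagged if >140 defines the category and not if >160 does. Diastolic 91-100 is flagged if >90 defines it and not if >100 does. If both limits apply together, the higher one adds nothing. The double limit affects everyone observed from age 17 if age at visit selects the row, and those enrolled at 17 if Baseline age does.

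**3. Reach, taking age at visit.**
- LDH and CK: 96 months / 12 = 8 years, and 10 + 8 = 18. Anyone aged 10 or older at Baseline who reaches the top exposure category has no limit by then.
- Table 2-1 records that all ongoing participants had completed at least Week 180 when Protocol Amendment 8 was implemented. 180 / 52 = 3.46 years and 15 + 3.46 = 18.46, so any of them enrolled at 15 or older was already 18.
- ALP: the year at age 17 holds 52 / 8 = 6.5 eight-weekly or 52 / 16 = 3.25 sixteen-weekly intervals, so about 6 or 3 visits without a limit for a participant on study throughout that year.

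**4. Denominator.** With n participants at a visit, k of them at an uncovered age and x flagged, the table as written shows x/n. The proportion among those who could be flagged is x/(n − k). The shown figure is therefore low by the factor (n − k)/n. The SAP does not give k.

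**5. Extraction check.** The LDH and CK rows recur in Section 13.2 (Amendment 2, Change #28). The vital-sign bands and double upper limits recur in Table 13-6 in Section 13.4, where one systolic low limit is garbled but the bands and upper limits agree. The ALP row has no second copy; it rests on Table 9-4 alone.

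**The case against.** **Baseline age may select the row.** The LDH/CK gap would then not arise. The ≥18y rows in a study enrolling ages 2-17 point to age at visit, but only moderately: the limits come from a general sponsor list that also has rows for infants, who cannot be enrolled. What stands is that the LDH/CK part is conditional. The ALP gap, the age-2 gap and the double limits survive either reading.

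**Other displays cover these values.** This largely stands. All laboratory and vital-sign data are listed and receive by-visit descriptive statistics. Hematology and biochemistry also get shift tables against central-laboratory ranges. The PDILI and Hy's Law criteria use multiples of the ULN, and Section 9.2.1 plans a hepatic event table. The primary safety variables, serious TEAEs and TEAEs leading to withdrawal of study drug, do not depend on these bands.

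**Stronger readings are tempting but not supported.**
- A reader might infer that some participants can never be flagged at all. Each gap concerns one parameter over one age interval.
- A reader might infer that every participant loses the ALP limit. Only those observed while 17 do (or, under Baseline age, those enrolled at 17); many younger enrollees need never reach that age on study.
- A reader might object that limits tighten at 17, so that an unchanged pulse of 51-59 or 101-119 becomes abnormal on a birthday. Age-banded criteria change at their boundaries by design; AST moves from >180 to >144 at 14 in the same table. For systolic pressure the step exists only if >140 governs; under >160 no value changes status. How strict adult limits should be is a clinical judgement, not an error in the plan.

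**Conclusion.** The point holds as a defect of definition. ALP has no limit from 17 to <18, LDH and CK have none from 18, and pulse and blood pressure have none from 2 to <3. From 17 years systolic and diastolic pressure each have two upper limits with no rule for choosing.

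Followed as written, the markedly-abnormal incidence tables count participants at an uncovered age as not abnormal for that parameter. They also leave systolic 141-160 and diastolic 91-100 open to either classification from age 17. The LDH/CK part assumes that age at visit selects the row; the rest does not. The number of participants affected cannot be worked out from the SAP. The age-2 gap is probably small and cannot occur in Russia.

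A reader might conclude that liver and muscle-enzyme safety is understated overall. The SAP does not support that, because the effect stops at the markedly-abnormal tables, flags and listings. It should still be corrected before the final analysis, since those tables cannot be read at face value in adolescents and young adults.

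**What to change.** 1. State in Sections 9.3 and 9.4.1 that age at the visit selects the row.
2. Make the ALP, LDH, CK, pulse and blood-pressure bands contiguous over all ages on study, with the sponsor taking the limits from its own source criteria. If no limit exists for an age, leave those participants out of that parameter's by-visit denominator and footnote the number left out.
3. For ≥17y, either name one upper systolic and one upper diastolic limit, or report the two as separately labelled tiers.

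Which limits are clinically right is for the sponsor to settle; the request is only that each age has one stated rule. The cost is edits to Tables 9-4 and 9-5, one added sentence in each of the two sections, and re-running the flags, tables and listings. No new data are needed.
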